5.1.3. Subgroup analysis of the primary outcome

A GEE model used for the analysis of the primary outcome in Section 5.1.1 will also be used for subgroup analysis of the primary outcome.

Subgroup analyses will be performed on age (< or \geq 35), ethnic (Han ethnicity or other

ethnicities), BMI ($<$ or $\geq 24\text{kg}/\text{m}^2$), presence of adverse pregnant history (Yes, No), exposure to smoking (Yes, No), total cholesterol ($<$ or $\geq 5.2 \text{ mmol}/\text{L}$), RBC folate status at baseline ($<$ or $\geq 400 \text{ ng}/\text{mL}$). Subgroup analyses may also base on categorized variables of the above continuous variable based on median value to make sample sizes of the categories comparable to achieve greater power.

Assessment of the homogeneity of treatment effect by a subgroup variable will be conducted by a GEE with the treatment, subgroup variable, and their interaction term as predictors, center as cluster, and the *P*-value presented for the interaction term.

Subgroup analysis will be performed on both ITT and PP populations.

5.2. Secondary Outcome Analysis

All secondary outcomes will be analysed as a superiority design and two-sided 95% CIs for the treatment differences in these outcomes between the two arms will be calculated and presented. Secondary outcome analyses will be based on the ITT population unless specified.

5.2.1. Analysis of binary secondary outcomes

Binary secondary outcomes will be analyzed with the same strategy and method that is used for the analysis of the primary outcome. GEE model will be performed with treatment as the only predictor and center as cluster effect using binomial distribution and log link function, from which the risk ratio between intervention and the control arm together with 95% CI will be derived.

Non-convergence will be dealt with using the same strategy as for the primary outcome analysis in Section 5.1.1

5.2.2. Analysis of continuous secondary outcomes

The continuous outcome will be summarised using number of subjects (n), mean, standard deviation (SD), minimum, and maximum by intervention group, and will be analysed by a GEE model with treatment as fixed effect, centre as cluster effect. The distribution will be normal distribution and link function is identity. Mean differences of outcome with their two-sided 95% CI between the two arms will be derived from the GEE model.

For repeated measurement variables, such as infant body weight at different visit, or maternal body weight during gestation, will be analyzed using linear mixed model with treatment, visit, interaction between treatment and visit as fixed effects, baseline measurement as covariate, cluster, and subject as random effects. SAS PROC GLMMIX will be used the data analysis.

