- Pregnant participants will receive a 75-g oral glucose tolerance test during 24-28 gestational weeks, and GDM will be diagnosed if any of the following criteria are met, based on the recommendations of the International Association of the Diabetes and Pregnancy Study Groups Consensus Panel: fasting glucose ≥ 5.1 mmol/L, 1-hour glucose ≥ 10.0 mmol/L, or 2-hour glucose ≥ 8.5 mmol/L.
- Time Frame: during 24-28 gestational weeks.
- Type: binary variable (Yes / No).

(8) Maternal gestational weight gain (kg)

- This outcome will be calculated as body weight at delivery minus weight before pregnancy (self-reported).
- Time Frame: from pre pregnancy to delivery.
- Type: continuous variable.

(9) Maternal weight gain (kg) at early gestation

- This outcome will be calculated as body weight at around 20 gestational weeks minus weight before pregnancy (self-reported).
- Time Frame: from pre pregnancy to 20 gestational weeks.
- Type: continuous variable.

(10) Occurrence of gestational hypertension

- Pregnant participants will undergo blood pressure measurements at each prenatal visit. Gestational hypertension will be diagnosed if systolic blood pressure ≥ 140 and/or diastolic blood pressure ≥ 90 mmHg, based on the recommendations of the International Society for the Study of Hypertension in Pregnancy (ISSHP).
- Time Frame: during pregnancy.
- Type: binary variable (Yes / No).

- (11) Maternal body weight (kg) at 6 months after delivery (Continuous variable)
- (12) Maternal HbA1c (%) at 6 months after delivery (Continuous variable)
- (13) Infant body weight (g) at birth, 42 day, 3 months, and 6 months (Continuous, repeated measurements)
- (14) Infant length (cm) at birth, 42 day, 3 months, and 6 months (Continuous, repeated measurements)
- (15) Infant body mass index (kg/m²) at birth, 42 day, 3 months, and 6 months (Continuous, repeated measurements)
- (16) Medical cost that relates with fetus and birth defects during pregnancy and after birth (Time Frame: from confirmation of pregnancy to one year old after birth) (Continuous variable)

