3.5. Sample Size

Sample size calculation was performed based on the primary outcome- the incidence of a composite rate of fetus, still birth, or birth defects. The proportion of primary endpoint was conservatively estimated to be 8% in the control arm according to two recent observational studies^{6,7} and 4% in the experimental arm (or 50% reduction) based on the findings of a meta-analysis of randomized intervention trials of folic acid supplementation intervention in folate-deficient population⁸. With cluster size of 100 subjects per centre, K coefficient of 0.23, a power of 85 % and a 5 % level of type I error, 22 clusters (2200 patients or 1100 in each arm) will be required. To allow for a 10 % dropout rate, at least 111 subjects (2446 patients or 1223 in each arm) will be recruited in each centre.

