5.1.2. Sensitivity analyses of the primary outcome

- **PP analysis of the primary outcome**

The same analysis of the primary outcome will be performed in the PP population using a GEE model (described in 5.1.1).

- **Covariate adjusted analysis of the primary outcome**

A GEE model used for the analysis of the primary outcome in Section 5.1.1 will also be used for covariate adjusted analysis using inverse probability of treatment weighting (IPTW) approach. The covariates will include age (continuous variable), ethnic (binary variable), body mass index (continuous variable), adverse pregnant history (binary variable), parity (continuous variable), exposure to smoking (mother or father's smoking status, binary variable), total cholesterol (continuous variable), and RBC folate level (continuous variable) at baseline to estimate adjusted risk ratio and 95% CI. Covariate adjusted analysis will be performed on both ITT and PP populations.

We will first calculate a propensity score with treatment as the dependent variable (1 for the experimental group and 0 for the reference group), and all covariates listed above as independent variables through a logistic regression model with a random effect for the center, and then perform an IPTW analysis (weighted GEE model). The adjusted risk ratio between the two groups and its two-sided 95%CI will be estimated.

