9.2. Appendix 2. FOID Study variable list

Appendix 2.1 Intervention trial variable list

NO	variable	
Pre-pregnancy		
1	hospital card number	T
2	Recruited number	T
3	Recruited date	D
4	Female name	T
5	Female height	N
6	Female weight	N
7	Female age	N
8	Male name	T
9	Male height	N
10	Male weight	N
11	Male age	N
12	Tel No	T
13	Community (basis for grouping)	N
14	Nutrient Interventions	B (1=intervention 0=control)
Nutrient first test		
15	Nutrient first test date	D
16	Serum folate	N
17	Red blood cell folate	N
18	Serum ferritin	N
19	VD(Vitamin D)	N
20	HCY(homocysteine)	N
21	Vitamin B12	N
22	LDL low density lipoprotein cholesterol	N
23	HDL high density lipoprotein cholesterol	N
24	TG total cholesterol	N
25	TC triglyceride	N
26	FBG(fasting blood-glucose)	N
27	Genotyping (BHMT (rs3733890), CBS (rs2850144, rs2851391), FIGN (rs2119289), MTHFD1 (rs2236225), MTHFR (rs1801131, rs1801133, rs3737965), MRT (rs1805087, rs28372871, rs1131450), MTRR (rs1801394, rs326119), RFC1 (rs1051266), and SHMT (rs1979277))	B
28	Clinical information (see Table 3)	-
29	Insufficient serum folate	B
30	Insufficient RBC folate	B

	Nutrient repetition measurement	
29	Nutrient repetition measurement date	D
30	Serum folate	N
31	Red blood cell folate	N
32	HCY (Homocysteine)	N
	Pregnancy	
33	Ultrasound image screen in mid-gestation	T
34	Report detail (positive)	B
35	Confirm image diagnosis	T
36	Therapeutic plan	T
37	birth defect diagnosis	T
38	Clinical information (see Table 2)	-

Note: T, text variable; D, The date type; N, Continuous variable; B, binary variable.

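### Maternal weight at 6 months after delivery (outcome 11) is analysed without the woman's recorded preconception weight, which gives up precision that costs nothing to recover

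*SAP*

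**What the plan says.** SAP section 2.2.2 lists outcome 11 as "Maternal body weight (kg) at 6 months after delivery (Continuous variable"). It is one absolute value. It is not a change from an earlier weight and, unlike infant outcomes 13 to 15, is not marked as repeated.

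Section 5.2.2 has two rules. A single continuous outcome "will be analysed by a GEE model with treatment as fixed effect, centre as cluster effect", with normal distribution and identity link; no other predictor is named. A repeated outcome gets a linear mixed model with "baseline measurement as covariate, cluster, and subject as random effects". The maternal example under the second rule is "maternal body weight during gestation", and the Table 4 shell in section 7 ends at delivery. Outcome 11 therefore comes under the first rule.

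No other section adjusts it. The weighted analysis in section 5.1.2, which includes body mass index, is headed "Covariate adjusted analysis of the primary outcome".

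Preconception weight is available. "Female weight" is item 6 of Appendix 2.1, in the pre-pregnancy block, and item 94 of Appendix 2.3. Section 2.2.2 also uses a prior weight for gestational weight gain (outcome 8), defined as "body weight at delivery minus weight before pregnancy (self-reported").

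**The concern.** Preconception weight is outcome 11's own baseline value, not a general prognostic factor, and would be expected to predict weight at 6 months strongly. Leaving it out keeps in the error term variation that the trial can already explain.

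The plan is also uneven. It subtracts prior weight for the gain outcomes and adjusts for baseline in the repeated-measures model, yet does neither for the one absolute maternal weight analysed on its own. With 11 centres per arm, some gap in preconception weight between the arms is to be expected, and the unadjusted contrast passes most of that gap on. At stake are a wider interval than necessary and a point estimate that is hard to interpret if the baseline table shows a visible weight difference.

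**Working it through.** **Plan's own figure.** The SAP gives no variance, correlation or detectable difference for outcome 11, so only the numbers per arm are borrowed from section 3.5. Those are coherent. The event rate is "conservatively estimated to be 8% in the control arm" and 4% in the experimental arm, with 100 per centre, k = 0.23, 85% power and 5% type I error (taken as two-sided). The Hayes-Bennett formula with t quantiles (df 20) gives 1 + 9.92 × [0.08×0.92/100 + 0.04×0.96/100 + 0.23²(0.08² + 0.04²)]/0.04² = 1 + 9.92 × 0.9645 = 10.57. That is 11 centres per arm, 22 in all. Normal quantiles give 9.66, or 10 per arm. Nothing below depends on this choice.

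**Inputs.** From the SAP: 100 women per centre, 1100 per arm. Assumed, because the documents give none: SD 8.5 kg; ICC 0.01; correlation r between preconception and 6-month weight 0.85, range 0.7-0.9; the same r within and between centres; no loss by 6 months.

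**Unadjusted standard error.** Design effect = 1 + 99 × 0.01 = 1.99. SE = √(2 × 8.5² × 1.99 / 1100) = 0.511 kg.

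**Adjusted standard error.** Adjustment leaves a fraction 1 − r² of the variance, so the SE is multiplied by √(1 − r²).

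| r | Variance removed (r²) | SE, kg | Equivalent sample size, 1/(1 − r²) |
|---|---|---|---|
| 0.70 | 49% | 0.511 × 0.714 = 0.365 | 1.96 |
| 0.85 | 72% | 0.511 × 0.527 = 0.269 | 3.60 |
| 0.90 | 81% | 0.511 × 0.436 = 0.223 | 5.26 |

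More than half of the variance is removed only if r exceeds √0.5 = 0.71. At r = 0.6 the figure is 36%.

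**Detectable difference at 80% power (r = 0.85).** 2.80 × 0.511 = 1.43 kg unadjusted and 2.80 × 0.269 = 0.75 kg adjusted. With t quantiles on 20 degrees of freedom (multiplier about 2.95) these become 1.51 and 0.79 kg; the ratio is unchanged.

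**Carry-through of a baseline gap.** With equal SDs, the unadjusted arm difference moves by about r kg per kg of baseline gap, so by 0.7-0.9 kg per kg. With the same SD and ICC at baseline, the chance gap has SE 0.51 kg. Its median size is 0.674 × 0.511 = 0.34 kg, and 0.5 kg is exceeded in about one randomisation in three.

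**Simulation.** GEE with exchangeable correlation, 22 centres of 100, SD 9 kg, baseline ICC 0.01, 200 runs per value of r. At r = 0.7 / 0.8 / 0.9 the slope of the unadjusted effect on the baseline gap was 0.61 / 0.80 / 0.92; after adjustment it was −0.09 / 0.00 / 0.02. The ratio of empirical SDs, adjusted to unadjusted, was 0.68 / 0.50 / 0.35. This is somewhat more favourable than √(1 − r²) because the simulation placed all centre variation in preconception weight.

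**Conditional error.** Given a baseline gap of b standard errors, the unadjusted z statistic under no effect is about normal with mean r × b and variance 1 − r². At b = 1.96 the chance of |z| > 1.96 is 21% / 26% / 33% for r = 0.7 / 0.8 / 0.9. At b = 1 it is 4% / 3% / 1%, below nominal.

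**Sensitivity.** Over SD 8-10 kg and ICC 0-0.05 the unadjusted SE runs from 0.34 to 1.04 kg. With r the same within and between centres, the proportional gain depends only on r.

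**The case against.** The strongest reply is that centres are randomised, so the treatment-only GEE is a valid analysis. A reader might infer that a chance weight gap is simply read as a treatment effect. The SAP does not support that: over all randomisations the estimate is unbiased, and the clustered standard error already includes chance differences between women and centres. The conditional error rates show the same thing, being above 5% for large gaps and below 5% for small ones. This part of the objection stands and limits the point to lost precision and to error conditional on the gap that occurs.

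A reader might also infer that the estimate mainly reflects which centres enrolled heavier women. On the assumed inputs it does not. Of the design effect of 1.99, the between-centre part is 100 × 0.01 = 1.00, about half; the rest is variation between women.

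Extending the change to weight-gain outcomes 8 and 9 is tempting too. Both already subtract weight before pregnancy, and weight at week 20 and at delivery also enters the baseline-adjusted mixed model. The argument does not carry over to them.

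Finally, the figures rest on assumed values, 1100 per arm was set for the primary outcome, and treatment-only models are also the stated policy for binary secondary outcomes. All true. None of it explains why section 5.2.2 uses the baseline for repeated weights and not for this one.

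**Conclusion.** The point holds as a matter of efficiency. Section 5.2.2 leaves a strong, already recorded baseline predictor out of the model for outcome 11. Under the stated assumptions, adjustment removes about 49-81% of the variance for a correlation of 0.7-0.9; at 0.85 the standard error falls from about 0.51 to 0.27 kg. The unadjusted estimate would carry about 70-90% of any realised baseline gap. The statement that most of the variance is left in needs a correlation above 0.71, which is plausible for the same woman's weight but is not given in the SAP.

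The planned analysis is not invalid or biased over randomisations. Outcome 11 is one of 16 secondary outcomes, has no sample-size claim and no row in the table shells, and does not bear on the trial's main conclusion, which section 5.1.1 draws from the primary-outcome GEE.

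**What to change.** Add one sentence to section 5.2.2: outcome 11 is analysed by the GEE with treatment and preconception weight as predictors and centre as cluster.

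Two details must be fixed with it:

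- **Which weight.** The SAP refers to a self-reported weight before pregnancy (section 2.2.2), a weight in the trial list (Appendix 2.1 item 6) and one in the routine preconception system (Appendix 2.3 item 94). Name one, for example the enrolment weight in Appendix 2.1 item 6.
- **Missing values.** Section 6.6 limits its imputation rule to the covariate-adjusted analysis. State that it also applies to this covariate, so that women without a recorded preconception weight are not dropped.

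Outcomes 8 and 9 stay as they are. The cost is one sentence and one variable already on the list, with no new data collection. The change should be made before unblinded data are examined.

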3.4. Randomization and Blind

Randomization will be performed based on recruited clusters. Stata 15 was used for randomisation code generation. Twenty-two community health care centres (clusters) will be allocated to an experimental arm or a control arm with 1:1 ratio using permuted block randomisation method with block size of 4. Randomisation list will be generated by an independent statistician.

The study is single blinded, the participants from the either arm will not know the medical care provided by the opposite arm. The study investigators who are involved in recruitment, the laboratory staff, and the dose-adjusting investigator (who was not involved in participant care) will remain blinded, since all the study outcomes will occur and observed at maternity hospitals. The investigator involved in intervention

and the statistician was not blinded, as unbinding was required to carry out statistical procedures.

The fetus and birth defects observers were maternity hospital ultrasound department and neonatologists and do their work according to the usual protocol and the data of outcomes were retrieved from the medical records. Therefore, all outcome assessments will be masked. The trial statistician will also be blinded regarding the treatment code when he develops the statistical analysis plan and writes the statistical programmers, which will be validated and completed using dummy randomisation codes. The actual allocation will only be provided to the study team after lock of the database.

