7. TABLE CONTENTS

Table 1: Summary statistics of baseline information.

Variable	Statistics	Treatment A (N=)	Treatment B (N=)	All (N=)
Age (year)	n			
	Mean			
	SD			
	<35			
	≥35			
Ethnicity	n			
	Han			
	Other			
Preconception Body Mass Index, kg/m ²	n			
	Mean			
	SD			
	<24 kg/m ²			
	≥24 kg/m ²			
Parity, time	n			
	1			
	≥2			
Presence of adverse pregnant history	n			
	Yes			
	No			
Exposure to smoking	n			
	Yes			
	No			

Table 2: Summary statistics of compliance of participants.

Variable	Statistics	Treatment A (N=)	Treatment B (N=)	All (N=)
RBC folate concentration before pregnancy	n			
	Mean			
	SD			
	Median			
	IOR			
<400 ng/ml	n(%)			
≥400 ng/ml	n(%)			
RBC folate concentration at the first antenatal visit	n			
	Mean			
	SD			
	Median			
	IQR			
<400 ng/ml	n(%)			
≥400 ng/ml	n(%)			

Table 3: Summary statistics of primary and secondary outcomes estimated by GEE model.

Primary and secondary binary outcomes	N(%)		GEE model analysis	
	Treatment A (N=)	Treatment B (N=)	Risk Ratio (95%CI)	p-value
Occurrence of fetus defects, still birth, and birth defects				
Occurrence of fetal defects				
Occurrence of birth defects				
Occurrence of abortion that related with congenital defects				
Occurrence of gestational hypertension				
Occurrence of maternal gestational diabetes				

Table 4: Summary statistics of secondary repeated measured outcomes estimated by linear mixed model.

Secondary repeated measured outcomes	Visit	n, mean (SD)		Mixed model analysis		
		Treatment A (N=)	Treatment B (N=)	A vs. B Mean difference (95%CI)	p-value	P-value from Treatment*time interaction test
Baby body weight	Birth					
	42 days					
	3 months					
	6 months					
Maternal body weight during gestation	Periconception					
	Gestational week 20					
	At delivery					

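### The repeated-measures model in SAP 5.2.2 leaves the covariance across visits unspecified, and its literal default risks miscalibrated by-visit intervals and treatment-by-time p-values

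*SAP*

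**What the plan says.** SAP 2.2.2, items (13) to (15), makes infant weight, length and BMI at birth, 42 days, 3 months and 6 months repeated-measures secondary outcomes. Section 5.2.2 analyses such variables, and maternal weight during gestation, in a linear mixed model with "treatment, visit, interaction between treatment and visit as fixed effects, baseline measurement as covariate, cluster, and subject as random effects". On software it adds only that "SAS PROC GLMMIX will be used the data analysis" (presumably PROC GLIMMIX).

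Section 5.2 promises that "two-sided 95% CIs for the treatment differences in these outcomes between the two arms will be calculated and presented". The Table 4 shell in section 7 has one row per visit for infant weight (four visits) and maternal weight (three time points). Its columns include a mean difference with 95% CI and a "P-value from Treatment*time interaction test". Length and BMI have no row in the shell but fall under the same model.

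Randomisation is by centre: "Twenty-two community health care centres (clusters) will be allocated to an experimental arm or a control arm with 1:1 ratio" (section 3.4).

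**The concern.** A mixed model takes its standard errors from its covariance structure. With a cluster effect and a subject effect, no further term, and one residual variance, three things are assumed:

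- the outcome is equally variable at every visit;
- any two visits are equally correlated;
- a centre's deviation is the same at every visit.

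Infant weight in grams may well spread out between birth and 6 months. If it does, a pooled variance makes the interval too wide at birth and too narrow at 6 months. Because centres are randomised, the treatment-by-visit contrast should be judged against how centres vary from visit to visit. The written model has no such term, so the contrast is judged against within-infant residual error.

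The other continuous outcomes in 5.2.2 use GEE with centre as the cluster, and the usual robust standard errors there tolerate a wrong working correlation. The repeated-measures paragraph names no such protection. At stake are the by-visit intervals and the interaction p-value, which are what Table 4 reports from this model.

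**Working it through.** **The plan's own figures.** The SAP gives no SD, ICC or centre-by-visit correlation for any growth outcome, so there is no figure for this model to reproduce. Its only between-centre figure is for the primary outcome: "With cluster size of 100 subjects per centre, K coefficient of 0.23" (section 3.5). That sample size does reproduce. The variance term is (0.08×0.92/100 + 0.04×0.96/100 + 0.23²×(0.08² + 0.04²))/0.04² = 0.9645. With t quantiles on 20 df the requirement is 10.57, so 11 centres per arm and 22 in all. The point below does not depend on it. All SDs, ICCs and correlations that follow are assumptions.

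**By-visit standard error.** With 11 centres per arm and n infants per centre:

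- literal model, every visit: SE = √[(2/11)(σ²_centre + (σ²_subject + σ²_error)/n)];
- truth at visit v: SE_v = √[(2/11)(σ²_centre,v + σ²_within,v/n)].

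Take SDs of 420/550/700/900 g, n = 90, ICC 0.01, and a centre effect that scales with the SD.

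- Truth at birth: √[(2/11)(0.01×420² + 0.99×420²/90)] = √[(2/11)(1764 + 1940)] = 26.0 g.
- Truth at 6 months: √[(2/11)(8100 + 8910)] = 55.6 g.
- Model: mean variance (176,400 + 302,500 + 490,000 + 810,000)/4 = 444,725. The within part is 0.99×444,725/90 = 4892. The centre part is 0.01×(2570/4)² = 4128. SE = √[(2/11)(9020)] = 40.5 g.
- Ratio of model to truth: 1.56 at birth and 0.73 at 6 months.

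**Simulation A** (2,000 runs per scenario; 11 centres per arm, 90 infants each, ICC 0.01, between-visit correlations 0.4 to 0.85, no true effect, complete data, no baseline covariate, t with 20 df):

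| Assumed SDs (g) | Centre effect | Coverage at birth | Coverage at 6 months | Interaction type I error |
|---|---|---|---|---|
| Model assumptions true | constant | 95% | 95% | 5.5% |
| 420/550/700/900 | scales with SD | 99.9% | 85.5% | 11% |
| 420/550/700/900 | constant | 97.9% | 91.2% | 7.5% |
| 420/480/560/630 | scales with SD | 98.9% | 91.5% | 8.4% |
| 420/480/560/630 | constant | 97.0% | 93.0% | 6.8% |

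Repeat runs of the second row gave 85.5–87.2% at 6 months and 11–13% for the interaction. Adding a centre-by-visit ICC of 0.005 raised the interaction error to 32–34%, and to 30% even with equal SDs.

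**Why the interaction test reacts so strongly.** Under no effect, the numerator of the F ratio has expectation σ²_error + n·σ²_centre×visit, but the denominator has σ²_error only. Take a typical correlation of 0.625 (midway between 0.4 and 0.85), so σ²_error is 0.375 of the total variance. The ratio is then 1 + 90×0.005/0.375 = 2.2. The 5% critical value for 3 df, 7.815 on the chi-square scale, becomes 7.815/2.2 = 3.55, which is exceeded about 31% of the time.

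**Simulation B** (100 infants per centre, otherwise the same kind of set-up):

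- Equal SDs, equal correlations, no centre-by-visit variation: coverage 95–96%, interaction error 5.0%. With unequal correlations: 95–96% and 6.3%.
- SDs 0.42/0.55/0.72/0.90 kg, ICC 0.02, constant centre effect: 97.6% at birth, 93.8% at 6 months, interaction 6.7%. Centre effect scaling with the SD: 99.6%, 86.4% and 15.3%.
- Equal SDs, between-visit centre correlation 0.8: coverage about 94–95%, interaction error 15.8%, 28.0% and 54.1% at ICC 0.01, 0.02 and 0.05.
- Mild SD growth as for length (1.7 to 2.2 cm), ICC 0: 98.5% at birth, 94.9% at 6 months, interaction 6.7%.
- Centre-level visit means with variances left free: coverage 93.9–96.2% and interaction error 4.5–5.7% in every scenario tried.

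**The case against.** A reader might infer that the SAP forces a single variance and that its intervals and interaction test will be wrong. The documents do not support that. Section 5.2.2 never mentions intercepts, a common variance or compound symmetry, and a structured residual or robust standard errors are not ruled out. The literal default is the natural reading, not stated text. The size of any error rests on quantities that the SAP does not give.

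The baseline covariate is a second fair objection. The simulations above omit it. If birth weight is the covariate, birth may not be an outcome visit and the over-coverage there has no counterpart, although Table 4 still has a birth row. With birth weight as covariate and the three later visits as outcomes, interaction error fell to 5.9–8.7% (steeper SDs) and 5.6–7.2% (milder SDs). Coverage at 6 months remained low, at about 87–91% and 91–92%.

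Third, the upper end of the 7–13% range needs a centre effect that scales with the SD, which is itself a form of centre-by-visit variation. The figure near 30% rests wholly on an assumed centre-by-visit ICC.

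Finally, the covariance choice affects standard errors and does not bias the treatment estimates, and the error at birth is conservative. All of these limits stand. They reduce the claim but do not remove it: either the literal model is run, or a structure is chosen later without prespecification.

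**Conclusion.** The point holds as a risk created by an under-specified model. Weight SD growth alone, over the assumed range, is enough to pull 6-month coverage clearly below 95% in most scenarios. The interaction test is only mildly liberal from SD growth with a constant centre effect, and seriously so once centres vary from visit to visit. If SDs are equal and there is no centre-by-visit variation, the by-visit intervals are sound.

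The direction follows from the model's structure. The magnitudes depend on assumed SDs, ICCs and correlations, and on complete, balanced data. Only secondary outcomes are touched; the primary GEE analysis in section 5.1.1 is not. A change is advisable because it is cheap and the affected quantities are the ones Table 4 reports.

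**What to change.** In section 5.2.2, replace the random-effects wording with:

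- an unstructured within-subject covariance across visits, or at minimum a separate residual variance per visit;
- centre random effects that may vary by visit (a cluster-by-visit term, with variance differing by visit where it can be estimated), since a common-variance term would still impose equal centre variance at all visits;
- a small-sample degrees-of-freedom method suited to 22 centres, such as Kenward-Roger;
- a statement of whether the birth measurement is the baseline covariate or an outcome visit, and likewise for periconception weight in the maternal model, with Table 4 made to match;
- a fallback for non-convergence: centre-level visit means for both the by-visit differences and the treatment-by-visit test (for example Hotelling's T²), so that Table 4 can still be completed.

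The fallback is the version whose calibration was checked above; the full mixed model with Kenward-Roger was not simulated. The cost is a few extra variance parameters, somewhat wider later-visit intervals and a few program lines. No new data are needed.
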